Short et al describes a quantifiable anatomical explanation for incomplete or failed anaesthesia from FNB or FICB in patients with #NOF. Several studies demonstrate that the FN block and FICB do not reliably block the obturator nerve or the lumbar plexus [16-22]. Distally, the high articular branches of the FN and AON are consistently located between the anterior inferior iliac spine and the iliopubic eminence [15]. The articular branches of the ON are located close to the inferomedial acetabulum. [15,23]. Subsequently the pericapsular nerve group block (PENGB) was designed to target the articular branches of the FN and AON by infiltrating the sub-psoas space at the level of the iliopubic eminence [23]. A case series of 5 consecutive patients with #NOF at Toronto Western Hospital was published in November 2018 and demonstrated the feasibility and efficacy of this block [23]. There is no published data describing the duration of analgesia provided by the PENG block.

The PENGB has subsequently been adopted by several practitioners at Lismore Base Hospital for the treatment of #NOF. We believe there is a study ongoing in peri-operative patients comparing PENGB to FICB in Toronto. We are not aware of any research into the utilisation of the PENGB in the emergency department setting. Searches of multiple study registries reveal no ongoing trials.

A retrospective study of patients that received regional anaesthesia for # NOF at LBH in the first 4 months of 2019 was performed. This data included 40 patients that received regional anaesthesia in ED, 6 of whom received a PENG block.

In this audit, patients' total opioid requirements from time of block to time of operation were recorded and converted to oral morphine equivalents using the ANZCA Faculty of Pain Opioid Calculator.

This audit found that patients receiving PENG blocks required fewer opioids pre operatively (mean = 22.67 mg) than did patients who did not receive a PENG block (FIB mean = 26.15 mg and FNB mean = 30.90 mg). Of note, patients receiving PENG blocks required fewer opioids in the 0-6 hours period immediately post block (mean = 3.00 mg) than did patients who did not receive a PENG block (FIB mean = 6.38 mg and FNB mean = 9.10). These results were not statistically significant ($p = 0.5$). The null hypothesis was retained. One adverse event relating to PENG blocks was documented in the records (failed block).

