- Treatment in this phase of the patient's journey will be decided by the acute pain service or duty anaesthetist. The investigators will have no influence over which repeat block the patient receives.

Block failure

- Defined as maximum pain score improvement of less than 1.5 out of 10.

Duration of analgesia from nerve block

- End of block effect defined as an increase in pain score to ≤ 1.0 from pre-block pain score in a patient who had a reduction in pain score of > 1.5 at any time.

Opioid Requirement

- Opioid intake will be measured by analysis of the electronic medication chart from the insertion of block until 12 hours have passed, or the patient is checked in to the operating theatre, whichever occurs first.
- This information will be converted to milligrams of oral morphine using the Faculty of Pain Medicine Opioid Calculator

Adverse events

In an effort to detect the incidence of adverse events, the investigators will:

- Perform a keyword search of the “Continuous Doc” feature of the electronic record, after the patient is discharged from the hospital.
 - Keywords:
 - Delirium
 - Sedation
 - Constipation / Constipated
 - Aspiration
 - Naloxone
- Review the electronic medication chart for use of:
 - Naloxone
 - Antibiotics

Surgery Waiting Time:

Time to surgery will be defined as the time from Triage in the Emergency Department to the time of Check In at Operating Theatre for operative fixation.

Data collection on our cohort for the purposes of the primary outcome will cease at the time of check in to the operating theatre or at 12 hours after the insertion of nerve block, whichever is sooner.

Mean, median and longest wait times will be recorded. This information will inform future practice at our hospital.

Data Collection and Storage

Primary Data Recording Methods:

Were discussed above and are summarised here:

- ❑ Documentation in the electronic medical record record (PowerChart / FirstNet / SurgiNet) as is usual practice for all patients treated in the emergency department and those admitted to the hospital
- ❑ Documentation on the paper SPIED Limb Observation Chart [Appendix 6] which is usual practice for patients admitted to the inpatient orthopaedic and surgical ward with fractured neck of femur. The standard chart has been modified for the SPIED study to include pain scores and pain score calculators.

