- ❑ Documentation on a paper form SPIED ED Data Form [Appendix 4] in the emergency department. This is additional to usual documentation and may be replaced by utilising Medical Surveys for data entry in the ED.
- ❑ Subjective Observed Patient Comfort During Nursing Score. May be completed in paper form [Appendix 7] or within Medical Surveys.

Data Governance

Data Storage:

The completed SPIED ED Data Form [Appendix 4] will be filed by clinicians in a folder within the Acute clinical area of the Emergency Department at Lismore Base Hospital. The SPIED ED Data Form will be the enrolment record.. Completed forms will be frequently collected by the investigators and stored securely with the ED Support Offices, which require swipe card access. This data will be stored for 5 years after the completion of data collection and then destroyed.

All other paper forms associated with the SPIED Study will form part of the patient's hospital record and will be treated accordingly.

Data Access:

- Investigators who are clinicians at Lismore Base Hospital have access to the patient's electronic medical records in the usual fashion as they would for day to day clinical work.
 - Investigators who access a patient's file for the purpose of data collection rather than clinical care, will create an electronic entry to document that they are accessing the file for the purposes of the SPIED study.
- In the event that any research funding is obtained, a research assistant may have access to Medical Surveys data and eMR as do the investigators.

Statistical Analysis

Primary Outcome:

Reduction in pain scores over the first 12 hours after nerve block. We will apply the following statistical tests:

- Student's t-test to compare the reduction in pain score of patients who receive a PENGGB compared to FNB and FICB
 - Subgroup analyses of the cognitively impaired and non-cognitively impaired population. These populations will have pain scored by the PAINAD and VAS respectively.
 - Subgroup analysis of FNB and FICB separately

Secondary Outcomes

- Onset of block. Defined as the time until the first pain score ≥ 1.5 less than the pre-block pain score.
 - T-test
- Subjective observed patient comfort during nursing cares
 - Chi Square test
- Patient Preference in the event of crossover
 - Chi Square test
- Rates of block failure. Defined as not achieving a reduction in pain score of $\geq 1.5 / 10$
 - Chi square test

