- Duration of analgesia. End of block effect defined as an increase in pain on movement score to ≤ 1.0 from pre-block pain score for that patient, in a patient who had a reduction in pain score on movement > 1.5 at any time.
 - T-test

Ethical Considerations

There are several ethical considerations in the design and implementation of this study. Throughout the study design process, the authors have consulted with key members of staff within our health service:

- ❑ *Director of Research: [name]*
- ❑ *Orthopaedic Clinical Nurse Specialist: [name]*
- ❑ *Acute Pain Service Clinical Nurse Consultant: [name]*
- ❑ *Surgical Clinical Nurse Educator: [name]*
- ❑ *Geriatric Medicine CMO: [name]*
- ❑ *Department of Anaesthesia Orthopaedic Special Interest Group: [name]*
- ❑ *Department of Anaesthesia research interest group: [name], [name]*
- ❑ *Pain Specialist: [name]*
- ❑ *LBH Nursing Infection Control: [name]*
- ❑ *Rural Research Education Manager: [name]*
- ❑ *Department of Emergency Medicine: Consultant group*
- ❑ *Emergency Department Clinical Nurse Educator: [name]*
- ❑ *Emergency Department Nurse Unit Managers: [name], [name]*
- ❑ *Director of Emergency Medicine Training: [name]*
- ❑ *NOF pathway working group headed by [name]*

Research merit and integrity

Merits of this research:

- We believe the PENGGB to have a superior anatomic basis for efficacy compared to other nerve blocks for neck of femur fractures. Early experience utilising the PENG block is promising.
- Early adoption of the PENGGB which, to our knowledge, has not been studied outside of Toronto, nor within an Emergency Department would place our institution in a leading position in the emergency management of # NOF.
- The generation of evidence supporting this therapy's safety and efficacy would be expected to increase its uptake both within our institution and at other institutions. A positive study would be expected to encourage further investigation in the form of a randomised clinical trial
- Generation of evidence that the PENGGB is inferior to the standard of care would appropriately discourage clinicians from changing their practice.

Integrity:

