Confirmation of the efficacy and safety of the PENGGB would be expected to lead to increased adoption of the technique in Emergency Departments around Australia. Should the PENGGB prove to be inferior to the present standard of care then this would also be valuable information to guide practitioners to continue to use the ultrasound-guided femoral nerve block to treat hip fractures in the emergency department. Probably, this study will confirm that the PENGGB is efficacious and safe without the statistical power to prove superiority to the existing standard of care. This will inform further research on the topic.

There recently is a significant research effort in Australia being directed to comparing the ultrasound-guided femoral nerve block to the ultrasound-guided FICB. There remains equipoise on this matter despite a randomised controlled double-blind trial of 100 patients published in 2018 [27]. There is also research in progress comparing the FICB as a single shot block versus a repeated or continuous infusion via a catheter inserted in the ED. If the PENGGB is the superior intervention, then these impressive research efforts might be better redirected to investigating the PENGGB.

Dissemination of results:

The principal investigator intends to disseminate the results of this study by:

- publication in a peer-reviewed journal approved by the college of emergency medicine and/or
- presenting results at the Australasian College of Emergency Medicine Annual Scientific meeting or Winter Symposium.

It is likely that co-investigators will disseminate the results of this study by presenting at relevant scientific meetings for Anaesthesia.

Appendices:

1. FirstNet NOF order set
2. Power Calculation Minimum
3. Power Calculation Maximum
4. SPIED ED Data Form
5. SPIED Enrolment Checklist
6. SPIED Limb Observation Chart
7. Subjective Observed Comfort During Nursing Care
8. nil
9. Inclusion-Exclusion Criteria
10. nil
11. SPIED Folder Contents
12. Patient Information and Consent

REFERENCES

1. Dyer, S.M., et al., *A critical review of the long-term disability outcomes following hip fracture*. BMC Geriatr, 2016. 16: p. 158.
2. Lystad, R.P., C.M. Cameron, and R.J. Mitchell, *Mortality risk among older Australians hospitalised with hip fracture: a population-based matched cohort study*. Arch Osteoporos, 2017. 12(1): p. 67.
3. ~~Dyer, S.M., et al., *A critical review of the long-term disability outcomes following hip fracture*. BMC Geriatr, 2016. 16: p. 158.~~

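### Onset, block failure and duration are defined by pain score alone, so relief that follows a post-block opioid is recorded as an effect of the block

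*Protocol*

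**What the plan says.** **Outcome definitions (Protocol, Secondary Outcomes and Statistical Analysis).**
- Onset: "Onset of block. Defined as the time until the first pain score" that is at least 1.5 points below the pre-block score.
- Block failure: "Defined as maximum pain score improvement of less than 1.5 out of 10".
- Duration: "End of block effect defined as an increase in pain on movement score to" within 1.0 of the pre-block value, in patients who had improved by more than 1.5 at some time. The outcome is titled as analgesia coming from the nerve block.
- Primary outcome: "Reduction in pain scores over the first 12 hours after nerve block", with a Student's t-test "to compare the reduction in pain score of patients who receive a PENGGB compared to FNB and FICB".

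**Opioids.** The Standard Order Set includes analgesia, and treatment is at the physician's discretion. Under Opioid Requirement, "Opioid intake will be measured by analysis of the electronic medication chart from the insertion of block until 12 hours have passed" or until theatre check-in, if that comes first. Intake is thus recorded over essentially the same window as pain. It enters none of the four definitions above, and Statistical Analysis lists no test for it.

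**Background audit.** PENG patients "required fewer opioids in the 0-6 hours period immediately post block (mean = 3.00 mg"), against 6.38 mg for FIB and 9.10 mg for FNB. Six of the 40 patients had a PENG block, the results were not significant (p = 0.5), and the null hypothesis was retained.

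**The concern.** Followed exactly, the definitions misclassify two kinds of patient:

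- The block does not work, an opioid is given, and pain falls by 2 points. The patient is recorded as having block onset at that time and is not a block failure.
- The block wears off, and an opioid is given before pain has returned to within 1.0 of the pre-block score. The patient is recorded as still having analgesia from the block.

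In both cases the outcome measures block plus opioid under a label that names the block. The background says that no data on the duration of PENG analgesia have been published, and an outcome defined this way cannot supply them.

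The comparison between blocks may also be affected. If residual pain prompts opioid use, the weaker block attracts more opioid and the pain scores move together. The protocol holds a related premise: Outcomes and Significance argues that a superior block should also spare opioids. Because the sample size is built on a one-sided non-inferiority test and the null hypothesis is comparable analgesia, narrowing works towards the conclusion that the blocks are comparable.

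**Working it through.** **1. The plan's own figure.** Inputs from Sample size and statistical power: one-sided 0.05, power 0.80, SD 2.4, means 4 and 2.5, ratio 1:2. The normal approximation for the smaller arm is (1 + 1/2) × (2.4 × (1.645 + 0.842) / 1.5)² = 23.7. That gives 24 + 48 = 72. Noncentral-t power is 0.797 at 24/48 and 0.809 at 25/49, so the stated 74 (25 + 49) reproduces. The sample size has no arithmetic error.

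**2. Assumed opioid model.** The documents give no opioid effect, so this is an illustration. Let X be a patient's pain reduction from the block alone. Every patient with X < 1.5 receives an opioid that adds e points of relief, with e = 1, 2 or 3, and no other patient does. The protocol does not say which block has mean 4 and which 2.5; here 4 is the better block.

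Share below 1.5:
- better block: Φ((1.5 − 4)/2.4) = 14.9%
- weaker block: Φ((1.5 − 2.5)/2.4) = 33.8%

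**3. Effect on the means.** The recorded mean is m + e × P(X < 1.5). For e = 2 this is 4.298 − 3.177 = 1.12.

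**4. Effect on the SD.** Raising only the low tail also reduces the spread. The recorded variance is 2.4² + e²p(1 − p) − 2e × 2.4 × φ((1.5 − m)/2.4). For e = 2:
- better block: 5.76 + 0.51 − 2.23 = 4.04, SD 2.01
- weaker block: 5.76 + 0.90 − 3.51 = 3.14, SD 1.77
- pooled over 25 and 49 patients: √((24 × 4.04 + 48 × 3.14)/72) = 1.86

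**5. Results at 25/49**, by noncentral t, with PENG the arm of 25. The power column takes PENG as the better block. The last column takes PENG as truly worse by 1.5 and reads 1.5 as the non-inferiority margin.

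| Assumed effect e | Recorded difference | Pooled SD | Standardised difference | Power | False non-inferiority |
|---|---|---|---|---|---|
| 0 | 1.50 | 2.40 | 0.625 | 0.81 | 0.05 |
| 1 | 1.31 | 2.10 | 0.624 | 0.81 | 0.10 |
| 2 | 1.12 | 1.86 | 0.604 | 0.79 | 0.20 |
| 3 | 0.93 | 1.69 | 0.551 | 0.72 | 0.36 |

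For the last column with e = 2, the deficit of 1.5 is recorded as 1.12, which leaves 0.38 of the margin unused. The pooled SD is then 1.93, because the arm sizes attach to the other block.

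**6. Block failure and onset.** With e = 2, the share recorded as never improving by 1.5 falls:
- better block: from 14.9% to Φ(−4.5/2.4) = 3.0%
- weaker block: from 33.8% to Φ(−3/2.4) = 10.6%

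The gap between blocks falls from 19.0 to 7.5 percentage points.

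**The case against.** **Pain under usual analgesia is a legitimate target.** The protocol describes appropriate management as multimodal, leaves care to the clinician, and collects opioid intake alongside pain. A reader might infer that the primary outcome is invalid because opioids contribute to it. The documents do not support that: block plus usual analgesia is a reasonable primary question, although the protocol should state it. The argument does not rescue outcomes named as onset of block, block failure and duration from the block.

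**The audit does not show different opioid use by block.** A reader might take the means of 3.00, 6.38 and 9.10 mg as evidence that it does. With six PENG patients, p = 0.5 and the null retained, they show plausibility only. Some doses may also be routine or habitual and unrelated to poor relief, so the direction of any bias is expected but not established.

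**The study need not lose much power.** Holding the SD at 2.4 while shrinking the difference by 20% to 1.20 would give power of 0.64. Under the model above the SD shrinks too, and power stays between 0.72 and 0.81. The fixed-margin non-inferiority reading is more sensitive, but its figures rest on the same assumed effect.

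**Sensitivity analyses are often left to an SAP.** That is fair, and the absence of one from the protocol is not itself the fault. The fault is that the protocol fixes three definitions which credit opioid relief to the block.

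**Conclusion.** The point holds for onset, block failure and duration. As written, each measures block plus any opioid given, under a name that attributes the result to the block. This follows from the text and needs no assumption.

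The effect on the comparison between blocks is conditional. If opioids go more to patients with poor relief, differences narrow and a comparable or non-inferior conclusion is favoured. The size cannot be obtained from the documents. Under an assumed effect of 1 to 3 points, confined to patients with a reduction below 1.5, the mean difference falls from 1.50 to between 1.31 and 0.93. The chance of passing a block that is truly worse by 1.5 then rises from 0.05 to between about 0.10 and 0.36. Reporting opioid intake separately helps interpretation but does not correct the three outcomes.

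**What to change.** Use the timed doses from the medication-chart review already planned under Opioid Requirement.

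1. **Onset and block failure.** Judge both, as block effects, on scores recorded before the first post-block opioid given for pain. Report patients who received an opioid first as a separate category, not as block onset.
2. **Duration.** Let the first opioid dose given for pain after onset also end block-alone analgesia.
3. **Primary outcome.** Keep the comparison on all scores and state that it measures block plus usual analgesia. Pre-specify one sensitivity analysis that accounts for post-block opioid use, for example with scores after the first dose replaced by the last score before it. Report it beside opioid intake by block, and consider it before claiming comparable analgesia.

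These changes affect definitions and analysis only, not patient care. They cost some protocol wording and chart extraction. Fewer patients will count as having block onset, and routine or habitual doses must be distinguished from doses given for pain. Two limits should be stated. If the opioid precedes any post-block score, carrying the last score forward imposes zero reduction. Opioid given before the block may still be acting at the early scores, and these rules do not remove that.

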1. SPIED Study Emergency Department Data Form [Appendix 4]
 - a. Emergency Department staff may choose to use this form in place of Medical Surveys should they prefer, or if there are logistical challenges encountered with Medical Surveys
2. Limb Observation Chart: [Appendix 6]
 - a. It is standard practice on the surgical ward for nursing staff to complete limb observations every 1-2 hours on patients with #NOF and record these on a limb observation chart.
 - b. This chart has been modified for the SPIED study to also record pain scores
 - c. Also includes pain score calculators for the VAS and PAINAD
3. Subjective Observed Patient Comfort During Nursing Cares [Appendix 7]

Primary outcome = reduction of pain score

VAS pain scores will be recorded at rest and on movement. Movement is defined as attempted hip flexion to 15 degrees. PAINAD scores will be single measure based on nursing observation.

This score will be documented at the following times:

- Prior to placement of nerve block in the emergency department
- 15, 30, 60 minutes post placement of block
- With routine limb observations on the surgical inpatient ward, approximately hourly

Data will be collected for 12 hours post nerve block (or the next documented score after 12 hours) or until the patient is moved to the operating room, whichever is sooner.

Sample size and statistical power

The rationale for sample size calculations:

- A reduction in visual analogue pain score of 13 mm (1.3/10) was established as being clinically significant by Todd et al in 1996 [26].
- A clinically significant difference between two treatments that reduce pain scores by 1.3/10 has not been well defined
- Cooper et al used 1.5/10 difference in pain scores as a definition of clinically significant difference between blocks [27].
- Newman et al found a standard deviation in pain score reduction of 2.4 in patients receiving regional analgesia for #NOF in 2013 [28]. This figure was used by Cooper et al for their power calculation in 2018.
- Cooper et al found standard deviations of 2.2 and 2.4 respectively for the FNB and FICB [27].
- A retrospective study of patients that received regional anaesthesia for # NOF at LBH in the first 4 months of 2019 was performed by co-investigators of this study. This data included 40 patients that received regional anaesthesia in ED, 6 of whom received a PENG block. Pain score documentation was not sufficiently reliable to inform power calculations for this observational study.

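### The t-test fixed for duration of analgesia has no valid value for blocks still working when scoring stops at 12 h or theatre, and the onset t-test describes responders only

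*Protocol*

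**What the plan says.** **Duration.** Under Statistical Analysis, Secondary Outcomes, the Protocol gives "End of block effect defined as an increase in pain on movement score" to within 1.0 of the pre-block score (my reading of the inequality), "in a patient who had a reduction in pain score on movement > 1.5 at any time". The test listed beneath it is a t-test.

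**Onset.** In the same list: "Onset of block. Defined as the time until the first pain score" at least 1.5 below the pre-block score. This is also given a t-test.

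**End of scoring.** The primary outcome section limits pain scores to 12 h, or the first score after that, "or until the patient is moved to the operating room, whichever is sooner". The Surgery Waiting Time section repeats the limit for the primary outcome: collection "will cease at the time of check in to the operating theatre or at 12 hours after the insertion of nerve block, whichever is sooner". Before the block and at 15, 30 and 60 minutes scores are scheduled; on the ward they are roughly hourly.

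**Patients without onset.** Block failure is a separate secondary outcome, "Defined as maximum pain score improvement of less than 1.5 out of 10", compared by chi-square.

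**Context.** The background states: "There is no published data describing the duration of analgesia provided by the PENG block". The choice of block is left to the treating clinician. The Secondary Outcomes section expects some patients to receive a repeat block before surgery. The Protocol assigns no value to a block whose end is not seen, and does not mention censoring.

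**The concern.** A t-test needs one number per patient. For a block still effective at 12 h or at theatre, the only thing known is that its duration exceeds the follow-up. The named test leaves two options. Dropping the patient removes the longest-acting blocks from each group. Entering the cut-off time as the duration measures follow-up in part rather than the block. The second option also makes the result depend on when patients go to theatre, and in an observational comparison nothing ensures that this is the same for both groups.

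At stake is a reported mean duration that is too short, and a comparison between blocks that may be diluted or driven by theatre scheduling. For onset, patients who never reach the 1.5-point drop have no onset time, so the t-test compares only those who responded.

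**Working it through.** **1. The plan's own figure.** The Protocol gives no figure for onset or duration. Its one sample size, 74 (25+49) for the primary outcome, reproduces closely: 1.5 × (2.4 × (1.645 + 0.842) / 1.5)² = 23.7, so 24 + 48 = 72 by the normal approximation. With 25 and 49 patients, the power by the t distribution is 80.9%. Nothing below changes it.

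**2. Effect of the cut-off (illustration).** The inputs are assumptions, because the documents give neither durations nor theatre times. Durations are counted from block insertion, with true means of 16 and 10 h. Theatre is uniform over 4 to 36 h, and follow-up is capped at 12 h. Let S(t) be the probability that the block still works at t, f(t) its density, and G(t) the probability of not yet being in theatre: 1 up to 4 h, then (36 − t)/32. All integrals run from 0 to 12 h.

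- Share censored: 1 − ∫ f·G dt
- Restricted mean to 12 h: ∫ S dt, which for an exponential with mean m is m(1 − e^(−12/m))
- Mean if cut-offs count as ends: ∫ S·G dt
- Mean if unfinished blocks are dropped: ∫ t·f·G dt / ∫ f·G dt

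| Exponential durations | Mean 16 h | Mean 10 h | Difference |
|---|---|---|---|
| Censored | 51% | 34% | |
| Restricted mean to 12 h | 8.44 | 6.99 | 1.45 h |
| Cut-off counted as end | 7.88 | 6.59 | 1.29 h |
| Unfinished blocks dropped | 4.98 | 4.58 | 0.41 h |

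| Gamma durations, shape 3 | Mean 16 h | Mean 10 h | Difference |
|---|---|---|---|
| Censored | 66% | 37% | |
| Restricted mean to 12 h | 10.36 | 8.48 | 1.88 h |
| Cut-off counted as end | 9.62 | 8.00 | 1.62 h |
| Unfinished blocks dropped | 7.57 | 6.72 | 0.85 h |

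Simulation of the same scenarios agrees to within 0.01 h (0.40, 1.29, 0.86 and 1.61 h). Counting cut-offs as ends also lowers each group's mean below its own 12-h restricted mean: in the exponential case by 8.44 − 7.88 = 0.56 h and 6.99 − 6.59 = 0.40 h.

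**3. A difference created by theatre times.** Assume equal durations in both groups (Weibull, shape 3, mean 8 h), exponential theatre times with means of 10 and 20 h, and a 12-h cap. The mean of the cut values is ∫ S(t)·e^(−t/c) dt, where c is the mean theatre time. This gives 5.28 h for c = 10 and 6.39 h for c = 20, a false difference of 1.11 h. In simulation with 41 and 84 patients (the Protocol's upper target of 125 with 41 PENG blocks), the two-sided 5% t-test rejects in about 44% of runs and log-rank in about 5%. When durations and theatre times are both equal across groups, no false difference arises: the t-test rejects in 4 to 5% of runs.

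**4. Onset.** Assume failure rates of 10% and 30%, and the same speed of onset among responders. The responders-only t-test rejects in about 5% of runs. Log-rank with failures kept as not reaching onset rejects in about 66%. The t-test shows no false difference here; it answers a narrower question, and the 66% reflects the difference in failure rates.

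**The case against.** **The 12-h horizon, not the test, causes most of the shrinkage.** A reader might infer that the t-test turns a true 6-h difference into 1.3 h. It does not. With scoring capped at 12 h, the proposed summary itself gives only 1.45 h in that scenario, so the loss due to counting cut-offs as ends is 0.16 h (0.26 h for the gamma case). If 12 h were the only cut, averaging the cut values would be the restricted mean to 12 h, and the t-test would lose little power: 43% against about 47% for log-rank (exponential), 90% against 93% (gamma). This stands. The serious distortions need unfinished blocks to be dropped, which the Protocol does not say it will do, or theatre times that differ by group, which is an assumption.

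**Onset.** A reader might infer that the onset result is biased. That is not shown. Failures are counted in their own outcome at the same 1.5-point threshold, and onset among responders beside a failure rate is a recognisable two-part description. What remains is that the onset comparison must not be read as covering all patients.

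**Importance.** Duration is not among the stated aims. The background notes only that published data are lacking, which does not make it a gap the study undertakes to fill.

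**A later analysis plan could change the test.** It could, but the Protocol does not leave the test open; it names one. Nor does it help that the Surgery Waiting Time sentence is worded for the primary outcome: duration uses the same pain scores, and the primary outcome section limits their collection in the same way.

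**Conclusion.** The point holds for duration. The named test cannot use a block whose end is not observed, and each workaround has a fault: dropping such patients cuts a 1.45-h restricted-mean difference to about 0.4 h in the exponential illustration, and counting cut-offs as ends understates the means and can produce a false difference of about 1.1 h when theatre times differ by group. These sizes rest on assumed durations and theatre times. The direction does not, provided some blocks outlast follow-up; with no published PENG duration, that cannot be ruled out.

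For onset the point is one of labelling and completeness. It would be wrong to conclude that the study's main result is undermined: these are secondary outcomes, and the primary analysis and the sample size of 74 are untouched. This should be fixed before analysis, but it is not a critical defect.

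**What to change.** - **Duration:** replace the t-test by Kaplan-Meier curves with a log-rank test or Cox model, and give the restricted mean to 12 h as the summary. Censor at the last score before theatre or 12 h. State the assumption that time to theatre is unrelated to block duration within group.
- **Repeat block before surgery:** state how it is handled. It may be given because the first block is wearing off, so treating it as ordinary censoring may be informative.
- **Spacing of scores:** consider interval-censored methods, since ward scores are roughly hourly and the end of effect is known only to lie between two of them.
- **Onset:** report the cumulative proportion with onset at 15, 30 and 60 minutes among all patients, with failures kept as not reaching onset. Alternatively, keep the t-test but label it a responders-only description to be read beside the block-failure rate.

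The cost is a revision of the statistical section. Score times and theatre check-in are already to be recorded, so no new data are needed.
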